The results of the phase 1 and 2 clinical trials confirm dose-proportionality for dasiglucagon pharmacokinetics, which is characterized by a fast absorption with a peak plasma concentration obtained after 35 minutes. Thereafter, the plasma concentration rapidly declines with an average half-life of 28 minutes. The median time to the maximum plasma concentration (C_{max}) was later for dasiglucagon than for GlucaGen (35 versus 20 minutes). Doses of 0.3 mg dasiglucagon and 0.5 mg GlucaGen and also 0.6 mg dasiglucagon and 1.0 mg GlucaGen were similar with regard to C_{max} . For C_{max} , the results indicated that 0.3 mg dasiglucagon was comparable to 0.5 mg GlucaGen (90% confidence interval (CI): 0.8167; 1.0068) and 0.6 mg dasiglucagon was comparable to 1.0 mg GlucaGen (90% CI: 0.8850; 1.1991).³ At these dose levels, the total exposures (AUC_{0-inf}) were higher for dasiglucagon compared to GlucaGen.

At all dose levels in the phase 2 trial, all patients achieved a plasma glucose level of at least 70 mg/dL as well as an increase in plasma glucose by at least 20 mg/dL within 30 min post-dose. The maximal observed time to reach the 20 mg/dL plasma glucose increase ranged from 15 to 27 minutes across doses and decreased as the dose increased. The pharmacodynamic responses of 0.6 mg of dasiglucagon and 1.0 mg of GlucaGen were comparable.³

Safety of dasiglucagon

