7.4.2 Treatments administered

Dasiglucagon is a stable peptide analog of human glucagon in a ready-to-use liquid formulation indicated for treatment of severe hypoglycemia in insulin dependent patients with diabetes mellitus. Dasiglucagon is in clinical development and has no marketing authorization as yet. GlucaGen is approved in the EU and US and is indicated for treatment of severe hypoglycemic reactions, which may occur in the management of insulin-treated children and adults with diabetes mellitus.

Patients in this trial have not previously been treated with dasiglucagon (ZP4207) and will be randomly assigned (1:1) to receive 1 of the following trial medications:

- 0.6 mg dasiglucagon
- 1 mg GlucaGen

Prior to administration of trial medication at all dosing visits patients must reach a target plasma glucose level of 70-150 mg/dL. If the patient presents with plasma glucose > 150 mg/dL, corrective amounts of fast acting insulin will be administered at the investigator's discretion. Plasma glucose measured after 20 and after 40 minutes should ensure that the patient has reached the targeted 70-150 mg/dL. If the patient presents with plasma glucose < 70 mg/dL glucose ingestion will be provided in order to reach target plasma glucose of 70-150 mg/dL documented by plasma glucose measurements after 20 and 40 minutes, respectively.

Following the first (Visit 2) and third (Visit 4) dose administration, patients must be fasting for 90 min after dosing. Following the 90-min blood sample draw after the administration of the first (Visit 2) and third (Visit 4) dose administration, patients may be treated individually in order to alleviate any potential side effects in order to minimize premature treatment discontinuation and consequently reduce the amount of missing data. This treatment can also be instituted immediately after the second dose administration (Visit 3), as pharmacodynamics will not be assessed at this visit.

In order to minimize the number of patients discontinuing treatment prematurely and consequently reduce the amount of missing data, the following treatment modalities may be used, as considered appropriate by the investigator:

At visit 2 and 4:

- 90 min after dosing patients will be allowed to eat and drink moderately to make them feel comfortable
- 90 min after dosing a moderate and individualized corrective dose of insulin to convert the induced hyperglycemia to euglycemia, after agreement with the investigator

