7.6.1 Immunogenicity measurements

Antibodies against dasiglucagon/glucagon will be measured at all visits after screening. During the treatment period (Visits 2, 3, and 4) samples will be collected pre-dose as well as at unscheduled dosing visits for ADA positive patients.

The ADA samples will be analyzed at a special laboratory (refer to Appendix 1). Samples collected at the planned visits will be analyzed in batches at three occasions during the trial and any positive results will immediately be communicated to the investigator in a blinded manner.

The clinical ADA assays have been validated in accordance with existing guidelines and recommendations.^{6,7,8,9,10}

Confirmed positive anti- dasiglucagon antibody samples, (treatment-induced or treatment-boosted) from anti-dasiglucagon antibody-positive patients will be evaluated for binding titer neutralizing potential and titer as well as cross-reactivity towards endogenous glucagon.

No further serum sampling will be needed as the ADA samples can be used for Nab analysis.

The *in vitro* neutralizing effect of antibodies will be measured using an assay^{9,12} based on glucagon receptor transfected human embryonic kidney cells. The calculated sensitivity in previous studies was about 51.8 ng/mL. The assay was also validated for recombinant glucagon with similar results.^{11,12} In case of a positive result in the Nab assay, a titer estimation will be performed. The cell-based Nab analyses will be performed by a special laboratory, BioAgilytix, Durham, NC, USA.

In vivo neutralizing effect will be evaluated by comparing PK and PD endpoints between ADA positive and ADA negative patients, further investigation may be performed by correlating ADA titer with PK and PD endpoints.

Residual and additional antibody serum samples may be stored until approval of market authorization by the health authorities. Further characterization of the antibody response may be requested by the health authorities.

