8.4 Hypoglycemia

Hypoglycemia will be regarded as an AE and recorded and documented on an AE Form.

Hypoglycemia is defined as a fall of plasma glucose below 3.9 mmol/L (70 mg/dL).

During the dosing visits, mild to moderate symptoms of hypoglycemia, or a blood glucose (BG) value less than a threshold of <2.8 mmol/L (50 mg/dL), corresponding to a plasma glucose (PG) value of <3.1 mmol/L (56 mg/dL), will be treated by i.v. glucose solution at the investigator's discretion according to best available medical practice. Treatment is to be repeated until BG value stabilized above the threshold limit again. BG measurements will only be done due to safety concerns. Insulin-induced hypoglycemia should be recorded as an AE.

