3. STUDY OBJECTIVES

The present trial aims to evaluate that immunogenicity risk with an assessment of the occurrence of ADAs and neutralizing ADAs, and of cross-reactivity with native glucagon, following repeated single doses of dasiglucagon by s.c. administration in T1DM patients. The trial further aims to evaluate the pharmacodynamics and pharmacokinetic responses and to correlate the consequence of an antibody response, if any, to pharmacodynamic and pharmacokinetic endpoints. The reference product in this trial is GlucaGen®, a recombinant human glucagon approved for the treatment of the severe hypoglycemic reactions that may occur in the management of insulin-treated children and adults with diabetes mellitus.

Primary objective

The primary objective is to describe the immunogenicity of repeated single doses of dasiglucagon and GlucaGen® following s.c. administration in T1DM patients.

Secondary objectives

The secondary objective consists of analyzing the safety, tolerability and pharmacodynamic response of repeated single doses of dasiglucagon following s.c. administration compared with s.c. GlucaGen® in T1DM patients.

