15. PHARMACOKINETIC (PK) AND PHARAMCODYNAMIC (PD) PROPERTIES

Pharmacokinetic and pharmacodynamic endpoints

Pharmacokinetic and pharmacodynamic characteristics are assessed by using the following endpoints:

1. Pharmacokinetics: Plasma dasiglucagon and GlucaGen® (glucagon) concentrations from 0-90 min after dosing will be evaluated based on the following endpoints: $AUC_{0-30\text{min}}$, $AUC_{0-90\text{ min}}$, C_{max} , t_{max} . Samples will be taken at visit 2 and visit 4 after first and third administration of trial medication. Samples will be collected pre-dose, and at 5, 10, 30, 60, and 90 min post-dosing.
2. Pharmacodynamics on plasma glucose concentrations after administration of first and third doses of trial medication. Samples will be collected pre-dose, and at 5, 10, 30, 60, and 90 min post-dosing:
 - Plasma glucose profiles over the period from 0-90 min after dosing will be evaluated based on the following endpoints: $AUE_{0-30\text{min}}$, $AUE_{0-90\text{ min}}$, CE_{max} , t_{max}
 - Achieving a plasma glucose increase of ≥ 20 mg/dL within 30 minutes after treatment

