16.1 PK and PD parameters

The pharmacokinetic metrics as listed below will be obtained from individual plasma concentration-time data by non-compartmental analysis using the computer programs WinNonLin® Version 5.4 or SAS Version 9.4.

The following PK parameters will be calculated for dasiglucagon and GlucaGen® analytes from the individual plasma concentration versus time profiles after each active treatment per visit.

Symbol	Definition	Calculation
C_{\max}	Measured maximum serum concentration after administration	Taken directly from analytical data, selected from individual concentration data
t_{\max}	Sampling time until reaching C_{\max}	Taken directly from analytical data, selected from individual concentration data
$AUC_{0-30\text{min}}$	Area under the concentration-time curve from zero up to the concentration at 30min	Linear trapezoidal rule for the ascending part of the concentration-time curve, logarithmic trapezoidal rule for the descending part.
$AUC_{0-90\text{min}}$	Area under the concentration-time curve from zero up to the concentration at 90min	Linear trapezoidal rule for the ascending part of the concentration-time curve, logarithmic trapezoidal rule for the descending part.

Table 2: Pharmacokinetic metrics

The following PD measures for glucose will be calculated from the plasma results for each treatment group and visit:

Symbol	Definition	Calculation
CE_{\max}	Change from baseline plasma glucose to maximum plasma glucose measured post-dose	Taken directly from analytical data, selected from individual concentration data
t_{\max}	Time to maximum change from baseline CE_{\max}	Taken directly from analytical data, selected from individual concentration data
$AUE_{0-30\text{min}}$	Area under the baseline-adjusted effect curve from zero up to the concentration measured at 30min	Linear trapezoidal rule for the ascending part of the effect-time curve, logarithmic trapezoidal rule for the descending part.
$AUE_{0-90\text{min}}$	Area under the baseline-adjusted effect curve from zero up to the concentration measured at 90min	Linear trapezoidal rule for the ascending part of the effect-time curve, logarithmic trapezoidal rule for the descending part.

Symbol	Definition	Calculation
Inc20 _{0-30min}	Increase of ≥ 20 mg/dL within 30 minutes after treatment	Binary variable derived from raw glucose concentration measured at 30min after dosing. In case glucose has reached at least 20 mg/dL the parameter is set to 'yes', otherwise to 'no'

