16.2 Data handling

Serial blood samples for pharmacokinetic and pharmacodynamic assessments will be drawn at the following intervals: pre-dose and 5min \pm 1min, 10min \pm 1min, 30min \pm 1min, 60min \pm 1min and 90min \pm 1min after start of dosing.

Summary tables for raw plasma concentrations, evaluation of concentration versus time data:

- i.) *For all pre-dose samples, the sampling time will be set to zero.*
- ii.) *For post-dose samples, the planned sampling time will be used in summary tables and the actual sampling times will be used for all figures of individual concentrations*
- iii.) *All pre-dose concentration values $< LLOQ^{[1]}$ will be set to zero.*
- iv.) *Post-dose concentration values $< LLOQ$ after t_{max} will be set to zero if there are no further concentrations $> LLOQ$ at later time points.*
- v.) *Post-dose concentration values $< LLOQ$ after t_{max} will be set to the lower limit of quantitation if there are further concentrations $> LLOQ$ at later time points.*
- vi.) *Missing post-dose values will not be replaced.*

Determination of PK/PD metrics:

- i.) *For all pre-dose samples, the sampling time will be set to zero.*
- ii.) *For post-dose samples, the actual sampling time will be used.*
- iii.) *All pre-dose concentration values will be set to zero.*
- iv.) *Post-dose concentration values $< LLOQ$ before t_{max} will be set to zero if there are no further concentrations $> LLOQ$ at later time points.*

^[1] LLOQ: Lower Limit of Quantification

- v.) *Post-dose concentration values < LLOQ before tmax will be set to the lower limit of quantitation if there are further concentrations > LLOQ at later time points.*
- vi.) *Post-dose concentration values < LLOQ after tmax will be ignored if there are no further concentrations > LLOQ at later time points.*
- vii.) *Post-dose concentration values < LLOQ after tmax will be set to the lower limit of quantitation if there are further concentrations > LLOQ at later time points.*
- viii.) *Missing post-dose values will not be replaced.*

PK and PD metrics will be determined by SynteractHCR. Plasma concentration data will be transferred from external laboratory (York Bioanalytical Solutions (YBS), MLM laboratories) to SynteractHCR as detailed in separate data transfer specifications.

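### The responder variable for a glucose rise of at least 20 mg/dL is programmed from the raw 30-minute glucose with no baseline, so practically every patient scores 'yes'

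*SAP*

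**What the plan says.** SAP section 15 lists the endpoint as "Achieving a plasma glucose increase of ≥ 20 mg/dL within 30 minutes after treatment", and protocol section 6 has the same wording. The Definition cell for Inc20 in SAP Table 3 (section 16.1) also speaks of an increase.

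The Calculation cell of that row is the programming instruction, and it differs. The variable is "derived from raw glucose concentration measured at 30min after dosing. In case glucose has reached at least 20 mg/dL", it is set to 'yes'; otherwise it is 'no'.

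Protocol 7.4.2 fixes the starting level: "Prior to administration of trial medication at all dosing visits patients must reach a target plasma glucose level of 70-150 mg/dL".

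SAP 16.2, under the rules for determining PK/PD metrics, adds as rule iii: "All pre-dose concentration values will be set to zero". The corresponding rule for the summary tables zeroes only pre-dose values below the quantification limit; this one has no such condition and names no analyte. In Table 3, CEmax is a change from baseline glucose and AUE is a baseline-adjusted area.

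SAP 20.1 and 20.2 declare no changes to endpoints or analyses.

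**The concern.** A change has been turned into a level. Since everyone starts well above 20 mg/dL, the coded variable is close to a constant and says nothing about whether the drug raised glucose.

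The endpoint has a purpose. Amendment 2 (section 3.2) added it to help bridge this trial to the pivotal efficacy trial. SAP section 3 aims "to correlate the consequence of an antibody response, if any, to pharmacodynamic and pharmacokinetic endpoints", and protocol 7.6.1 says the in vivo "neutralizing effect will be evaluated by comparing PK and PD endpoints between ADA positive and ADA negative patients". A variable that is 'yes' for everyone cannot show a blunted response in an antibody-positive patient.

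Program checking is not a safeguard. SAP section 6 and Appendix B check output against the plan and its derivation rules, so a program that follows the Calculation cell would pass.

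**Working it through.** **Inputs.** Pre-dose glucose 70-150 mg/dL (protocol 7.4.2). Endpoint: rise of at least 20 mg/dL within 30 minutes (protocol 6, SAP 15). Coded rule: 30-minute glucose of at least 20 mg/dL (SAP Table 3). Samples pre-dose and at 5, 10, 30, 60 and 90 minutes (SAP 15). The plan states no expected responder rate, so there is no figure to reproduce.

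**1. What a 'no' requires.** Let b be the pre-dose glucose and d the change at 30 minutes. The coded rule gives 'yes' when b + d ≥ 20, that is, when d ≥ 20 − b.
- b = 70: 'no' only if glucose falls by more than 50 mg/dL.
- b = 110: by more than 90 mg/dL.
- b = 150: by more than 130 mg/dL.

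The cut-off of 20 also lies 56 − 20 = 36 mg/dL under the level in protocol 8.4, where a low value "corresponding to a plasma glucose (PG) value of <3.1 mmol/L (56 mg/dL), will be treated by i.v. glucose solution".

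**2. Test profiles.** Intended rule: highest of the 5-, 10- and 30-minute values minus pre-dose ≥ 20.

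| Profile (mg/dL) | Coded rule | Intended rule |
|---|---|---|
| Flat at 70 | yes | no |
| Flat at 150 | yes | no |
| 150 falling to 56 at 30 min | yes | no |
| 110 rising by only 19 | yes | no |
| 110, then 131 at 10 min, 125 at 30 min | yes | yes |

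The last row shows why the earlier samples matter: the rise at 30 minutes is 125 − 110 = 15, but 131 − 110 = 21 was reached within the window.

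**3. Behaviour over a range of effects.** Simulation with 1,000,000 draws per scenario. Assumptions: b uniform on 70-150, d normal, rules compared at the 30-minute sample. Results for SD 20 mg/dL:

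| Mean change | Coded 'yes' | True rise ≥ 20 |
|---|---|---|
| −20 | 99.3% | 2.3% |
| 0 | 99.95% | 15.8% |
| 20 | 100% | 49.9% |
| 40 | 100% | 84.1% |
| 60 | 100% | 97.7% |

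The lowest coded rate in any scenario (SD 10 to 30) was 96.9%, at a mean fall of 20 with SD 30, where the true rate was 9.1%.

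**4. Effect on the reported rate.** Exact (Clopper-Pearson) 95% intervals, with five failures in an arm assumed:
- 45 per arm (planned completers): 40/45 = 88.9% (75.9-96.3), reported as 45/45 = 100% (92.1-100).
- 56 per arm (112/2, expected treated): 51/56 = 91.1% (80.4-97.0), reported as 56/56 = 100% (93.6-100).
- No failures: no change.

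**5. Rule iii, if applied literally to glucose.** A corrected formula becomes glucose − 0 ≥ 20, which is the coded rule again; the simulated rates are identical. CEmax is overstated by b, 70-150 mg/dL. For AUE by linear trapezoid at nominal times, the first interval adds 5 × b/2 = 2.5b and each later minute adds b:
- 0-30 min: 2.5b + 25b = 27.5b, or 1,925 to 4,125 mg·min/dL.
- 0-90 min: 2.5b + 85b = 87.5b, or 6,125 to 13,125 mg·min/dL.

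The SAP uses the logarithmic rule on the descending part. For the profile 110/115/130/170/190/160 the 0-90 excess is then 9,647 instead of 87.5 × 110 = 9,625, an immaterial difference. PD tmax is unaffected.

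**The case against.** **The intent is clear.** The variable's name, its Definition cell, SAP 15 and protocol 6 all say increase, so this looks like a drafting slip that a careful programmer would query. That is fair as to intent, but the Calculation cell is the instruction that is programmed and checked, and its reference to the raw value argues against an implied subtraction.

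**Little depends on it.** The endpoint is secondary and descriptive, the primary endpoint is untouched, and glucose values are tabulated and listed, so Inc20 can be recomputed. In phase 2 all patients had "an increase in plasma glucose by at least 20 mg/dL within 30 min post-dose", so the true rate may be near 100% anyway. All of this stands. It limits the likely change in the reported figure but does not make the rule informative: it would return about 100% whatever happened.

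**The antibody comparison is not built.** SAP 16.3, 16.4 and Appendix C list no PD table by antibody status, and CEmax and AUE would show a blunted response better. That stands as a limit on the immediate harm, though both documents state the aim.

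**Rule iii was written for drug assays.** Its list speaks of quantification limits, and applying it to glucose would contradict Table 3. This largely stands: the rule is a contradiction to clarify, not a certain loss of baseline.

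**The denominator may not be 45.** The PK/PD set is drawn from treated patients, so about 56 per arm is possible. The conclusion is the same with either number.

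**Conclusion.** The Inc20 derivation is wrong as written and must be corrected before analysis. It contradicts its own Definition cell, SAP 15 and protocol 6, and with dosing at 70-150 mg/dL it cannot record a plausible non-responder. Nothing elsewhere in the SAP corrects it. Confidence is high on this part and moderate on rule iii, where the text needs a glucose exemption but a programmer might supply it unprompted.

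The size of the error in the report depends on the unknown true rate: nil if every patient responds, about 11 percentage points if 5 of 45 do not. That example and the simulated means and SDs are assumptions, not figures from the documents. The rule iii amounts apply only if the rule is used on glucose.

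**What to change.** **SAP Table 3, Inc20, Calculation cell.** Set 'yes' if the highest glucose at the nominal 5-, 10- and 30-minute samples minus the measured pre-dose glucose of the same visit is at least 20 mg/dL; otherwise 'no'. Restoring the baseline is the correction. Using all three samples is a second change, made to match the endpoint's 30-minute window, and should be labelled as such.

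**Missing values.** In line with SAP section 9 (no imputation), Inc20 is missing, not 'no', when the pre-dose glucose is missing, or when the 30-minute sample is missing and neither earlier sample shows the rise.

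**SAP 16.2, rule iii for PK/PD metrics.** State that it applies to dasiglucagon and glucagon concentrations only, and that the observed pre-dose glucose at each visit is the baseline for CEmax, AUE and Inc20.

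**Cost.** One table cell, one sentence in 16.2 and the matching programming. No new data are needed.

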16.2 Data handling

Serial blood samples for pharmacokinetic and pharmacodynamic assessments will be drawn at the following intervals: pre-dose and 5min \pm 1min, 10min \pm 1min, 30min \pm 1min, 60min \pm 1min and 90min \pm 1min after start of dosing.

Summary tables for raw plasma concentrations, evaluation of concentration versus time data:

- i.) *For all pre-dose samples, the sampling time will be set to zero.*
- ii.) *For post-dose samples, the planned sampling time will be used in summary tables and the actual sampling times will be used for all figures of individual concentrations*
- iii.) *All pre-dose concentration values $< LLOQ^{[1]}$ will be set to zero.*
- iv.) *Post-dose concentration values $< LLOQ$ after t_{max} will be set to zero if there are no further concentrations $> LLOQ$ at later time points.*
- v.) *Post-dose concentration values $< LLOQ$ after t_{max} will be set to the lower limit of quantitation if there are further concentrations $> LLOQ$ at later time points.*
- vi.) *Missing post-dose values will not be replaced.*

Determination of PK/PD metrics:

- i.) *For all pre-dose samples, the sampling time will be set to zero.*
- ii.) *For post-dose samples, the actual sampling time will be used.*
- iii.) *All pre-dose concentration values will be set to zero.*
- iv.) *Post-dose concentration values $< LLOQ$ before t_{max} will be set to zero if there are no further concentrations $> LLOQ$ at later time points.*

^[1] LLOQ: Lower Limit of Quantification

- v.) *Post-dose concentration values < LLOQ before tmax will be set to the lower limit of quantitation if there are further concentrations > LLOQ at later time points.*
- vi.) *Post-dose concentration values < LLOQ after tmax will be ignored if there are no further concentrations > LLOQ at later time points.*
- vii.) *Post-dose concentration values < LLOQ after tmax will be set to the lower limit of quantitation if there are further concentrations > LLOQ at later time points.*
- viii.) *Missing post-dose values will not be replaced.*

PK and PD metrics will be determined by SynteractHCR. Plasma concentration data will be transferred from external laboratory (York Bioanalytical Solutions (YBS), MLM laboratories) to SynteractHCR as detailed in separate data transfer specifications.

